There will also be a sensitivity analysis of the primary, key secondary, and mortality outcomes to evaluate the effect of concomitant therapy including experimental treatment and off-label use of marketed medications that are intended as treatment for COVID-19 and are given to patient prior to and during the study. A blinded review of the concomitant medication data will be performed by the medical monitor to identify medications that fall into any of the following categories of “Medications of Interest”:

- Antivirals
 - Protease inhibitors
 - Polymerase inhibitors
- Potential Treatments for COVID-19
 - Hydroxychloroquine/Chloroquine
 - Other
- Corticosteroids
- RAS Inhibitors
- Other anti-inflammatory drugs
 - Monoclonal Antibodies Targeting Cytokines
 - Other Biologic Therapies

Summaries of subjects who report use of the categories and subcategories of therapies/treatments will be provided. Note that after the blinded review of the medications, additional categories/sub-categories may be defined and/or categories/sub-categories may be combined.

In addition, the sensitivity analyses will consider the following categories (individually):

- Any Medication of Interest
- Hydroxychloroquine/Chloroquine
- Corticosteroids
- RAS Inhibitors

- Other Anti-Inflammatory Drugs

For the recovery analyses, subjects will be censored at the time of medication/therapy initiation. If a subject recovered prior to use of any of the medications/therapies, then the subject will still be counted as a recovery in the sensitivity analysis. For the analysis of the key secondary outcome, if a subject reports use of any of the medications/therapies prior to their Day 15 assessment, then the subject's last clinical status score prior to medication/therapy use will be used as their Day 15 outcome. For the mortality analyses, subjects will be censored at the time of medication/therapy initiation. All medication of interest sensitivity analyses will exclude subjects with a baseline ordinal score of 6.

In addition, time to recovery will be explored within the following concomitant medication use subgroups:

- Pre Enrollment Corticosteroid Use (Yes/No)
- Post Enrollment Corticosteroid Use (Yes/No)
- Post Enrollment Dexamethasone Use (Yes/No)

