6.5. Missing Data

All attempts will be made to collect all data per protocol. Any data point that appears to be erroneous or inexplicable based on clinical judgment will be investigated as a possible outlier. If data points are identified as outliers, sensitivity analyses may be performed to examine the impact of including or excluding the outliers. Any substantive differences in these analyses will be reported.

For time to event outcomes, subjects who are lost to follow-up or terminate the study prior to Day 29 and prior to observing/experiencing the event will be censored at the time of their last observed assessment. Subjects who die prior to observing/experiencing the event will be censored at Day 29.

For the analysis of the key secondary outcome, subjects who are discharged but are subsequently re-admitted prior to Day 15 without a reported clinical score, their clinical score will be imputed at 7, which is the highest value for a hospitalized subject.

For the analyses of the secondary outcomes that involve clinical score (i.e. the key secondary outcome and time to improvement), if a subject is discharged from the hospital (but not to hospice or other end-of-life care) without a previously or concurrently reported clinical score of 1 or 2, then their clinical score at the time of discharge will be imputed as 2, which is the highest value for a non-hospitalized subject. If a subject terminates early from the study while they are

hospitalized or completes the study while still hospitalized, the last observed clinical score assessment will be used as their final assessment.

For the modified version of the ordinal score described in Section 4.3, if a subject is discharged from the hospital without a previously or concurrently reported clinical score of 2 or 3, then their clinical score at the time of discharge will be imputed as 3, which is the highest value for a non-hospitalized subject.

For the analyses of the secondary outcomes described in Section 3.3, the following imputation rules will be used for subjects who are lost to follow-up, terminate early from the study, or do not have further outcome data available after discharge for any reason:

- NEWS Total score (any missing study day)
 - If the subject dies or is discharged to hospice or other end-of-life care prior to the missing study day, the worst NEWS score (20) will be imputed

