Treatment Arm-Categorical Baseline Ordinal Score Interaction	Interferon beta-1a + RDV (N=X)	4	X.XX	X.XX, X.XX	0.000	
	Placebo + RDV (N=X)					
	Interferon beta-1a + RDV (N=X)	5	X.XX	X.XX, X.XX		
	Placebo + RDV (N=X)					
	Interferon beta-1a + RDV (N=X)	6	X.XX	X.XX, X.XX		
	Placebo + RDV (N=X)					

HR is the ratio of the hazard of recovery in each treatment group estimated from the indicated model. The ratio is Interferon beta-1a + RDV to Placebo + RDV.

HR for the 'Any Baseline Ordinal Score' group is the hazard ratio from the stratified Cox Model.

For the Fine-Gray model, subjects who die prior to any observed recovery are coded as experiencing a competing risk.

Covariate adjustment is by age, duration of symptoms prior to randomization, baseline d-dimer, and baseline CRP values as continuous covariates. This analysis is restricted to subjects with a baseline ordinal score of 4 or 5. High-sensitivity CRP values are excluded from this analysis.

Estimates are HR and CIs from Fine-Gray or interaction Cox models. For the interaction models, HRs are calculated at the level of each individual OS category.

a: P-values are from the likelihood ratio test.

Programming Notes:

For the “Treatment Arm-Baseline Ordinal Score Interaction”, the severity covariate will be treated as a categorical variable.

Tables with similar format as Table 12:

Table 13: Time to Recovery by Treatment Group within Subgroups – mITT Population, Baseline Ordinal Score of 4 or 5

Table 14: Time to Recovery by Treatment Group and Baseline Ordinal Score: Readmittance Sensitivity Analysis – mITT Population, Baseline Ordinal Score of 4 or 5

Table 15: Time to Recovery by Treatment Group and Baseline Ordinal Score: Medications of Interest Sensitivity Analysis – mITT Population, Baseline Ordinal Score of 4 or 5

Programming Notes for Table 13:

This table is restricted to subjects with a baseline ordinal score of 4 or 5. The “Disease Severity” and “Analysis Population” columns will be removed. A “Subgroup” column will be inserted to the left of the “Treatment Group” column. This table will not display the “Any...” rows. The elements for the “n” and “Median Time to Recovery” columns will display “-”. This table will include the statin/ARB/AECI use, corticosteroid use, and dexamethasone use (see Section 6.4) subgroups. P-values will not be included in this table. Disease severity subgroups will not be included in this table.

Programming Notes for Table 14 and Table 15:

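### Three supporting analyses in SAP 6.4 and 6.5 use post-randomisation information as if it were baseline or Day 15 data, and the drug-start rules are undefined for earlier users

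*SAP*

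**What the plan says.** **Medication-of-interest sensitivity analyses (SAP 6.4).** They cover listed drugs given before or during the study.

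- Day 15: if use is reported before the Day 15 assessment, "the subject's last clinical status score prior to medication/therapy use will be used as their Day 15 outcome".
- Recovery: "For the recovery analyses, subjects will be censored at the time of medication/therapy initiation". The one exception is recovery before use.
- Mortality: "For the mortality analyses, subjects will be censored at the time of medication/therapy initiation".
- Population: "All medication of interest sensitivity analyses will exclude subjects with a baseline ordinal score of 6".

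Death after drug start is not mentioned. The general rule in SAP 6.5 is "Subjects who die prior to observing/experiencing the event will be censored at Day 29", and neither section says which prevails. The notes to Tables 15 and 80 repeat the drug-start censoring and add a count of users. The Table 18 rows do neither.

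**Steroid subgroups.** SAP 6.4 explores time to recovery by corticosteroid use before enrolment, and also by "Post Enrollment Corticosteroid Use (Yes/No") and "Post Enrollment Dexamethasone Use (Yes/No"). The notes to Table 13 confirm: "This table will include the statin/ARB/AECI use, corticosteroid use, and dexamethasone use (see Section 6.4) subgroups".

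**Baseline laboratory values.** SAP 3.3.1 defines an efficacy baseline as the last value before randomisation. When that value is missing for d-dimer or CRP, SAP 6.5 falls back on another pre-treatment value and then on the earliest post-treatment one. Tables 45 and 46 use the imputed results.

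**Drug categories.** SAP 6.4 lists RAS inhibitors as a category to be analysed individually. The lists for Tables 15, 18 and 80 omit it, and those tables exclude ARBs and ACE inhibitors from the any-medication row.

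**The concern.** These tables are meant to show whether the findings hold up against other therapy and baseline differences. Each problem weakens that use.

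- Whether a patient starts a steroid after randomisation is itself an outcome. If interferon changes worsening, or changes the clinician's decision to start, the Yes and No groups no longer compare like with like between arms.
- A post-dose laboratory value used as baseline makes the change at that visit zero whatever the drug did. It could also enter, as a baseline covariate, the adjusted models that SAP 6.4 plans with d-dimer and CRP.
- A Table 18 row that reports users' status at drug start under a Day 15 title invites misreading. Some subjects who died by Day 15 may appear there as alive.
- For a drug started before enrolment there is no earlier score, because scoring begins at randomisation, and the censoring time falls before time zero. Two programmers could produce different tables.

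**Working it through.** **The plan's own figure.** Protocol Appendix C 9.2 gives N = 396 for an odds ratio of 1.75 at 85% power. The Whitehead formula, 12(z_α/2 + z_β)² / [λ²(1 − Σp³)], with Scenario 1 and λ = ln 1.75, gives 394. The Scenario 1 distributions are therefore a sound base for illustration.

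**Frozen Day 15 scores.** The documents give no rate of medication use, so every share is assumed. Take the Scenario 1 control distribution and its counterpart at odds ratio 1.75. Move a share u of both arms to one score, independently of arm and outcome, and refit the proportional-odds model.

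| Share frozen | 20% | 40% | 60% |
|---|---|---|---|
| All frozen at 5 | 1.45 | 1.29 | 1.18 |
| All frozen at 4 | 1.50 | 1.35 | 1.25 |
| Range, Scenarios 1–5, score 5 or 4 | 1.41–1.60 | 1.24–1.49 | 1.14–1.40 |
| Frozen at 5, but deaths kept at 8 | 1.46 | 1.29 | 1.20 |

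**Deaths alone.** Control deaths are 2.0%. Treated odds are (0.02/0.98)/1.75 = 0.01166, or 1.15%. The average is (20.0 + 11.5)/2 = 15.8 per 1,000. If 30/60/90% of those who die had started a listed drug, 4.7/9.5/14.2 per 1,000 are scored as alive. Moving only these to score 5 or 4 leaves the odds ratio at 1.749–1.750 (1.744–1.750 over all five scenarios). The attenuation comes from freezing users, not from the deaths.

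**Post-enrolment steroid split.** Assumed daily model, 400,000 subjects per arm. At score 5, recovery is 14% and worsening 3% per day. After worsening, return is 12% and death 3.5% per day. Drug start is 2% per day, rising to 15% after worsening. With no treatment effect, about 92% recover and 4.2% die by Day 28.

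| Assumed effect of treatment | Recovery HR, all | Steroid Yes | Steroid No |
|---|---|---|---|
| None | 1.00 | 1.00 | 1.00 |
| Start rate ×1.25 (20% v 23% users) | 1.00 | 1.05 | 1.04 |
| Start rate ×2 (20% v 31% users) | 1.00 | 1.18 | 1.16 |
| Worsening ×1.6 | 0.91 | 0.84 | 0.99 |

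In rows two and three both subgroups show a benefit that does not exist. In row four the No group hides a harm. For noise, exp(±1.96 × 2/√E) around 1.00 gives 0.80–1.25 at an assumed E = 300 recoveries and 0.85–1.17 at 600. Most of these shifts lie within chance.

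**Post-treatment baseline.** If the Day 3 value stands as baseline, change at Day 3 is x − x = 0. With a share s of an arm substituted in this way, and the rest unaffected, its mean Day 3 change is multiplied by (1 − s): 0.98, 0.95 and 0.90 at s = 2%, 5% and 10%.

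**Prior users.** Protocol Appendix C 6.5.1 permits earlier COVID-directed therapy if it stops at enrolment, and 6.5.2 records medications from 7 days before. SAP 6.4 itself defines a pre-enrolment steroid subgroup, so such subjects are expected. The ordinal scale starts at randomisation (Protocol Appendix C 8.1.2.2; SAP 4.3). The only handling of an earlier start is a display convention in the listings.

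**The case against.** The strongest reply is that these are secondary matters, handled by choice. The medication and steroid analyses are sensitivity or exploratory work in baseline score 4 or 5. Censoring at drug start deliberately removes what happens after another therapy begins, and Tables 15 and 80 say so and count the users. Tables 51 and 52 give use by arm and day. The d-dimer and CRP fallback applies only when a baseline is missing, and Tables 45 and 46 have no between-arm difference column. Some prior therapies are excluded at entry, SAP 6.4 allows categories to be combined after blinded review, and statins, ARBs and ACE inhibitors have their own subgroup analysis.

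Most of this stands, and it limits the point. It does not justify a causal-looking hazard ratio within a post-randomisation group, a post-dose baseline, or unlabelled rows in Table 18.

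A reader might go further and infer that counting the dead as alive distorts the Day 15 result. The arithmetic does not support that: deaths alone leave the odds ratio at about 1.75. A reader might also infer that those deaths must be scored 8. That is debatable, because counting later deaths but not later improvement mixes two estimands. Nor is it safe to infer that the Day 29 death rule in SAP 6.5 overrides drug-start censoring. The notes to Tables 15 and 80 point the other way, and SAP 6.4 is silent.

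**Conclusion.** The point holds for supporting tables only. Two stated rules can give a biased or meaningless number: treatment hazard ratios within the two post-enrolment steroid groups, and the post-treatment laboratory baseline. The first is biased only if treatment affects steroid start or the worsening that prompts it; with neither, the hazard ratios stay at about 1.00. The second makes one visit's change zero for each affected subject. Whether the substituted value also reaches the covariate-adjusted models is not stated.

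The Table 18 problem is one of labelling. Under the assumed 20–60% use the odds ratio moves well away from 1.75, so agreement or disagreement with the main result cannot be read directly from those rows. The prior-user gap and the RAS-inhibitor mismatch are wording defects.

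Some may read this as a threat to the trial's conclusions. It is not: the primary, main key secondary and main mortality analyses, the alpha and the sample size do not depend on any of these rules. All sizes above rest on assumed usage and course.

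**What to change.** 1. **Steroid subgroups.** Take the two post-enrolment rows out of the Table 13 treatment effects, or show them as descriptive and non-causal. Keep the pre-enrolment subgroup.
2. **d-dimer and CRP.** Do not use a post-dose value as baseline; leave baseline and change missing. Say that the same holds for the covariate-adjusted models. The cost is slightly fewer subjects with a change score.
3. **Table 18.** Retitle the medication rows as sensitivity analyses, footnote users' scores as status at drug start, and show by arm the number frozen and the deaths among them. Scoring those deaths as 8 is optional and barely moves the odds ratio, so the footnote is needed either way.
4. **Tables 15 and 80.** Add that censoring at drug start may be informative, and state in SAP 6.4 whether it takes precedence over the SAP 6.5 death rule.
5. **Rules.** Apply the freeze and the censoring only to starts after randomisation. Reconcile the RAS-inhibitor category between SAP 6.4 and the shells for Tables 15, 18 and 80.

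All of this is SAP wording, footnotes and count rows. No new data are needed.

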6.5. Missing Data

All attempts will be made to collect all data per protocol. Any data point that appears to be erroneous or inexplicable based on clinical judgment will be investigated as a possible outlier. If data points are identified as outliers, sensitivity analyses may be performed to examine the impact of including or excluding the outliers. Any substantive differences in these analyses will be reported.

For time to event outcomes, subjects who are lost to follow-up or terminate the study prior to Day 29 and prior to observing/experiencing the event will be censored at the time of their last observed assessment. Subjects who die prior to observing/experiencing the event will be censored at Day 29.

For the analysis of the key secondary outcome, subjects who are discharged but are subsequently re-admitted prior to Day 15 without a reported clinical score, their clinical score will be imputed at 7, which is the highest value for a hospitalized subject.

For the analyses of the secondary outcomes that involve clinical score (i.e. the key secondary outcome and time to improvement), if a subject is discharged from the hospital (but not to hospice or other end-of-life care) without a previously or concurrently reported clinical score of 1 or 2, then their clinical score at the time of discharge will be imputed as 2, which is the highest value for a non-hospitalized subject. If a subject terminates early from the study while they are

hospitalized or completes the study while still hospitalized, the last observed clinical score assessment will be used as their final assessment.

For the modified version of the ordinal score described in Section 4.3, if a subject is discharged from the hospital without a previously or concurrently reported clinical score of 2 or 3, then their clinical score at the time of discharge will be imputed as 3, which is the highest value for a non-hospitalized subject.

For the analyses of the secondary outcomes described in Section 3.3, the following imputation rules will be used for subjects who are lost to follow-up, terminate early from the study, or do not have further outcome data available after discharge for any reason:

- NEWS Total score (any missing study day)
 - If the subject dies or is discharged to hospice or other end-of-life care prior to the missing study day, the worst NEWS score (20) will be imputed
 - If the subject is discharged (not to hospice or other end-of-life care) prior to the missing study day, a NEWS score of 2 will be imputed.
 - If the subject is neither dead nor discharged, use the previous NEWS total score, or missing component-carried forward for all subsequent visits.
- Days of Non-invasive ventilation/high-flow oxygen:
 - If the subject's clinical status scale is 6 at the last observed assessment, then the subject will be considered to be on non-invasive ventilation/high-flow oxygen through Day 29. The endpoint will be total days when assessments are available plus all imputed days following the last observed assessment.
 - If the subject is not on non-invasive ventilation/high-flow oxygen at the last observed assessment, then the subject will be considered to not be on non- invasive ventilation/high-flow oxygen for the remainder of follow-up. Thus, no additional imputed days will be added to the number of days recorded on available assessments.
- Days of ventilation/ECMO:
 - If the subject's clinical status scale is 7 at the last observed assessment, then the subject will be considered to be on ventilation/ECMO through Day 29. The endpoint will be total days when assessments are available plus all imputed days following the last observed assessment.
 - If the subject is not on ventilation/ECMO at the last observed assessment, then the subject will be considered to not be on ventilation/ECMO through Day 29. Thus, no additional imputed days will be added to the number of days recorded on available assessments.
- Days of Oxygen:
 - If the subject's clinical status score is 5, 6, or 7 at the last observed assessment, then the subject will be considered to be on oxygen through Day 29. The endpoint will be total days when assessments are available plus all imputed days following the last observed assessment.

- If the subject is not on oxygen at the last observed assessment, then the subject will be considered to not be on oxygen through Day 29. Thus, no additional imputed days will be added to the number of days recorded on available assessments.
- Days of Hospitalization
 - If the subject is discharged and no further hospitalization data are available, then the subject will be assumed to not have been readmitted. Thus, no additional imputed days will be added to the number of days recorded on available assessments. If a subject dies while hospitalized, the number of days of hospitalization will be imputed as 28 days.
- Lab Efficacy (d-dimer and CRP)
 - If results are not available for any visit day (s), but are available for visits before or after that visit, the average of the two nearest visits will be imputed for all missing visits between them. If a subject dies or is otherwise lost to follow-up, their last available observation will be carried forward. If baseline is missing, another pre-treatment dose will be used, or the earliest post-treatment dose will be used.

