8.1.2 Efficacy Assessments

8.1.2.1 Measures of clinical support, limitations and infection control

The subject's clinical status, which is largely measured by the ordinal scale and NEWS, will be captured on each study day while hospitalized through Day 29 (+ 6-day window) or day after death whichever comes first. The ordinal scale will also be captured on the day after discharge from the hospital. This will be done so that discharge and death are accurately recorded and captured in the eClinical system. For subjects who received oxygen by nasal cannula or CPAP ventilatory support at night at home prior to having COVID-19, sites should assign a recovery ordinal scale score of 1 or 2 when discharged to home after recovery. The assignment of category 1 versus category 2 will depend on whether they have new or increased physical limitations post-COVID-19 and/or if they have new or increased home oxygen requirement compared with the pre-COVID-19 time period.

It is important to capture all deaths that occur during the study as this is one of the outcomes of the study. Death is a category on the ordinal scale. If a subject dies during the study, an ordinal scale assessment should be completed for the day after death because the ordinal scale captures the worst clinical assessment for the previous day. If a subject dies within the window of the final study visit (i.e., Day 29 + 6-day window), complete an ordinal scale assessment on the day after death.

If a subject is discharged prior to Day 15, clinical status is collected on Day 15 and 29 if the subject returns for an in-person clinic visit or by phone, home visit or remote telehealth procedure as per institutional standards if an in-person visit at the clinical trial site is not possible. Clinical status will also be captured on Day 22 during a phone call or remote telehealth visit. Unlike the NEWS, the ordinal scale can also be evaluated over the phone or by a remote telehealth procedure if the discharged subject is unable to return to the clinical trial site for visits on Day 15 and 29 as well as on Day 22.

Except for Day 1, when the ordinal scale and the NEWS is captured at the time of randomization, a site should try to complete the ordinal scale and the NEWS at approximately the same time each day. Ideally, complete the ordinal scale concurrently with NEWS just prior to study product administration, as time permits. The following measures are recorded for the ordinal scale:

- Hospitalization.

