3.3.2. Recovery and Time to Recovery

The primary efficacy and one of the key secondary outcome measures is the time to recovery assessed through Day 29 + 6 days. Recovery will be defined as having a value of 1, 2, or 3 on the clinical status 8-point ordinal scale. The time to recovery will be defined as the elapsed time (in days) from randomization to the earliest day at which a subject reaches recovery. Note that since clinical status assessments are recorded as defined in Section 4.3, the day that is being assessed (not necessarily the day the response is collected) will be used to determine the timing of events. For example, a subject with a score of 5 recorded on Days 1-3 and a score of 3 recorded on

Day 4 will have a time to recovery equal to 3 days. It is also possible that a subject has a clinical status score > 3 reported for a particular day but was subsequently discharged on the same day. Such cases and other special cases will be reviewed by the Endpoint Review Committee or the NIAID Medical Officer, or her designee(s), to make the determination of whether the subject should be considered recovered in analyses. Subject data to be reviewed as part of this determination will include the reported clinical status scores while hospitalized, where the subject was discharged to (e.g. private residence, rehabilitation facility, long-term care/nursing home, comfort and care), and any information regarding readmittance. Subjects discharged to hospice or other end-of-life care will not be considered recovered. Additional information may be solicited to assess recovery.

Any subjects that are lost to follow-up or terminated early prior to an observed recovery will be censored at the day of their last observed assessment. Subjects who complete follow-up but do not experience recovery will be censored at the day of their Day 29 visit. All deaths that occur on or before Day 29 (and prior to any observed recovery) will be considered censored at 28 days. Note that we do not expect many subjects to worsen after discharge. However, we will evaluate whether any discharged subjects subsequently experience a worse clinical status and sensitivity analyses will be conducted accordingly. For these analyses, subjects who recover but are later readmitted for COVID-19 will not be considered a recovery but will instead be censored at 28 days.

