3.3.4. Time to Clinical Status Improvement

Additional analyses will evaluate the time to improvement of at least one point on the clinical status 8-point ordinal scale. That is, improvement will be defined as a decrease of at least one point on the 8-point scale compared to the baseline value (e.g. from 5 to 4; from 5 to 3) and the time to improvement will be defined as the elapsed time (in days) from randomization to the earliest day of observed improvement. Note that since clinical status assessments are recorded as defined in Section 4.3, the day that is being assessed (not necessarily the day the response is collected) will be used to determine the timing of events.

For analyses of this outcome, imputation of the clinical score may be performed following the rules described in Section 6.5.

Any subjects that are lost to follow-up or terminated early prior to an observed improvement will be censored at the day of their last observed assessment. Subjects who complete follow-up but do not experience improvement will be censored at the day of their Day 29 visit. All deaths that occur on or before Day 29 (and prior to any observed improvement) will be considered censored at 28 days.

An alternative definition of improvement will also be used where improvement will be defined as a decrease of at least two points on the 8-point scale compared to the baseline value (e.g. from 5 to 3; from 5 to 2). The timing and censoring definitions will follow similarly to the above.

3.3.5. Time to Discharge or NEWS of ≤ 2

The time to discharge or NEWS of ≤ 2 will be defined as the elapsed time (in days) from baseline to the earliest day at which either of the following occur:

- Discharge from hospital, unless discharged to hospital or end-of-life care.
- Reported NEWS of ≤ 2 which is maintained for 24 hours

For the latter bullet, to meet this criterion, scores of ≤ 2 must be reported on consecutive study visits. The timing of the event will be set to the day of the second assessment. Subjects who enroll with a baseline NEWS of ≤ 2 must be discharged from the hospital to meet this endpoint.

All deaths or discharge to hospice or other end-of-life care that occur before discharge or before an observed NEWS of ≤ 2 will be considered censored at 28 days.

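### Time to improvement can count a hospice discharge as a success, and SAP 6.5 does not say how a transfer to another acute-care hospital is scored

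*SAP*

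**What the plan says.** **Hospice.** SAP 3.3.4 counts improvement as a drop of at least one point (alternatively two) from baseline, timed to the first day it is seen. On deaths it says "All deaths that occur on or before Day 29 (and prior to any observed improvement) will be considered censored at 28 days"; hospice is not mentioned. Other sections do deal with it:

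- Recovery (SAP 3.3.2): "Subjects discharged to hospice or other end-of-life care will not be considered recovered".
- Time to discharge or low NEWS (SAP 3.3.5): a hospice discharge before the endpoint is censored at 28 days. The bullet defining a qualifying discharge reads "Discharge from hospital, unless discharged to hospital or end-of-life care".
- NEWS imputation (SAP 6.5): missing days after a hospice discharge get the worst score, 20. For a patient discharged elsewhere "prior to the missing study day, a NEWS score of 2 will be imputed".

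Protocol Appendix C 8.1.2.1 adds: "The ordinal scale will also be captured on the day after discharge from the hospital".

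**Discharge without a score.** For the Day 15 and time-to-improvement outcomes, the main rule in SAP 6.5 covers a patient who leaves hospital with neither a 1 nor a 2 on record: "then their clinical score at the time of discharge will be imputed as 2, which is the highest value for a non-hospitalized subject". Hospice is carved out in the condition attached to that rule, which begins "if a subject is discharged from the hospital (but not to hospice or other end-of-life care) without a previously or concurrently reported clinical score" and goes on to name those two values. The next paragraph gives the matching rule for the Modified Recovery scale: impute 3 at discharge, with no hospice exception.

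**Two neighbouring rules in SAP 6.5.** For the key secondary outcome, when a discharged patient is readmitted before Day 15 and has no score, "their clinical score will be imputed at 7, which is the highest value for a hospitalized subject". A patient who leaves or completes the study while still in hospital keeps the last observed score. Transfer to another hospital is not mentioned, and no order of precedence is given.

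**The concern.** An exit to hospice is a clinical failure, and the SAP treats it so in three places. In time to improvement, the same exit can become an early success. The patients are foreseeable: the retention section of Appendix C (5.6.2) describes requests to stop study products because of terminal illness as a common situation in ACTT-1.

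A transfer to another acute-care hospital may be a step up in care. If it is logged as a discharge, the trigger for imputing 2 is met precisely because the patient never reached 1 or 2. An unstated choice between a near-best score, the worst living score and the last observed score should not be left to programming, particularly when one of the outcomes is a key secondary endpoint.

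If such exits are more frequent in one arm, these outcomes would understate that arm's deterioration.

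**Working it through.** **1. Hospice, rule by rule.** Take a patient with baseline score 5 who goes home with hospice care, is recorded as 2 by the site, and dies before Day 29.

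| Outcome | Result under the SAP |
|---|---|
| Time to recovery (3.3.2) | Not recovered |
| Time to discharge or low NEWS (3.3.5), endpoint not already met | Censored at 28 days |
| NEWS on missing days (6.5) | 20, the worst score |
| Time to improvement (3.3.4) | Event: 5 − 2 = 3 categories, so both definitions are met |
| Day 15 status | 8 if dead by then; 2 if alive and that is the score used |

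The death does not reverse the improvement, because only deaths before any observed improvement are held to 28 days. From the other enrolled baselines the drop is 4 − 2 = 2 and 6 − 2 = 4, so both definitions are met in every case.

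**2. Modified Recovery scale.** Take a hospice discharge with no 2 or 3 reported. The rule imputes 3, giving drops of 4 − 3 = 1, 5 − 3 = 2 and 6 − 3 = 3. The one-category definition is met from every baseline and the two-category definition from 5 and 6. Here the imputation itself creates the event.

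**3. Transfer.** Take a baseline-5 patient whose last score is 6 when moved on Day 5 to another acute-care hospital.

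- If logged as a discharge: score 2 on Day 5, an improvement of 5 − 2 = 3 categories. NEWS is 2 on missing days, and no hospital days are added if no later data arrive.
- If treated as an unscored readmission: Day 15 score of 7. This rule covers the key secondary outcome only.
- If treated as leaving the study while hospitalized: last observed score, 6, and no improvement.

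A score collected at the Day 15 visit replaces imputation for the Day 15 endpoint (SAP 3.3.3). It does not cancel an improvement event already set at discharge.

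**4. Size on the Day 15 odds ratio.** The plan's own figure comes first. The formula in Appendix C 9.2 is N = 12(z_α/2 + z_β)² / [λ²(1 − Σp³)], with p the category probabilities averaged over the arms. For Scenario 1, odds ratio 1.75, 85% power and two-sided 0.05: 12 × (1.960 + 1.036)² ≈ 107.7; λ² = (ln 1.75)² ≈ 0.313; Σp³ ≈ 0.127. So N ≈ 107.7 / (0.313 × 0.873) ≈ 394, against the stated 396.

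A proportional-odds model was then fitted to the expected proportions after moving an assumed share of categories 5-7 to category 2 in both arms. In Scenario 1, categories 5-7 hold 7 + 2 + 1 = 10% of controls.

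| Share of 5-7 scored 2 | Scenario 1: OR (power at 396) | Scenario 5: OR (power at 396) |
|---|---|---|
| 0% | 1.750 (85.2%) | 1.750 (88.3%) |
| 5% | 1.748 (85.0%) | 1.735 (87.3%) |
| 10% | 1.745 (84.7%) | 1.720 (86.2%) |
| 25% | 1.738 (84.1%) | 1.677 (82.7%) |
| 50% | 1.727 (83.0%) | 1.608 (75.8%) |

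For an imbalance with no true effect, moving 1% of one arm (4.6 of about 462) from 5 to 2 gives an odds ratio of about 1.02, and 2% (9.2 patients) gives about 1.05. By the same formula the standard error of the log odds ratio at N = 923 is about 0.12, so ln 1.05 ≈ 0.049 is roughly 0.4 of a standard error. The N for this analysis is below 923 by the number enrolled at baseline 6, who are excluded.

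**5. Size on time to improvement.** Each affected patient moves from no event by Day 28 to an event at the time of exit. The documents give no basis for a count.

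**The case against.** The strongest reply is that much of this is inference. SAP 6.5 never mentions transfer, and exclusion criterion 1 names discharge and transfer as separate events, so discharge in 6.5 need not cover a transfer. Day 15 normally rests on a collected score, obtainable by phone, and sites are told to keep following patients admitted elsewhere. Time to improvement is supplemental, and its table shell (Table 20) shows a hazard ratio and interval without a p-value. The key secondary p-value is reported only if the primary result is significant.

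Most of that stands, and it rules out several stronger readings that a reader might infer:

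- That SAP 6.5 scores transfers as 2. It is silent; 2 is only the literal result if the transfer is logged as a discharge.
- That the main imputation rule gives hospice patients a 2. Its own clause excepts them. The causes are the missing exclusion in 3.3.4 and the missing exception in the Modified Recovery rule.
- That a living hospice patient scored 2 on Day 15 is an error. A patient at home with new limitations fits category 2 as defined; ranking that patient lower is an estimand choice.
- That SAP 3.3.5 deliberately excepts transfers. Its reference to a hospital as destination may be a slip for hospice, the word used at the end of that section.
- That these rules conceal the concern the DSMB raised in score 6. The key secondary analysis excludes score 6, and the DSMB reported no signal in scores 4 and 5. Time to improvement is tabulated for score 6, but death and progression to ventilation are analysed separately.

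The hospice point on the main scale also depends on a 2 being recorded. The form asks for the worst state of the previous day, so a site may enter the inpatient score on the day after discharge. That limits how often the problem arises; it does not supply the exclusion. The destination review in SAP 3.3.2 concerns recovery, and committee review of endpoints (Appendix C 9.3) is optional.

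**Conclusion.** The point holds in three parts. First, SAP 3.3.4 lets a recorded 2 after hospice discharge count as improvement, against the SAP's own handling elsewhere. Second, the Modified Recovery rule in 6.5 lacks the hospice exception that stands one paragraph earlier. Third, 6.5 leaves transfer to another acute-care hospital undefined, with three possible scores and no precedence.

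The primary endpoint is untouched. For Day 15 the expected effect is small: with equal mis-scoring in both arms, 1.75 reads 1.73-1.75 in Scenario 1 and 1.61-1.74 in Scenario 5. A shift of 1-2% in one arm moves a null odds ratio to about 1.02-1.05, in a direction that cannot be known beforehand. These ranges rest on assumed frequencies, because the documents give none. The main exposure is time to improvement, where each affected patient changes from a failure to an early success.

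**What to change.** - **SAP 3.3.4:** state that discharge to hospice or end-of-life care is not an improvement, whatever score is recorded afterwards, and censor at 28 days as 3.3.5 does.
- **SAP 6.5, Modified Recovery rule:** add the hospice exception already in the main rule.
- **SAP 6.5, transfer:** treat transfer to another acute-care hospital as continued hospitalization. Use the score from the receiving hospital or, failing that, the last inpatient score, and apply the same principle to the NEWS and hospital-day rules.
- **SAP 6.5, precedence:** state which rule applies when more than one fits.
- **SAP 3.3.5:** check whether the destination named in the discharge bullet should be hospice.

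The cost is a few sentences and one derivation flag. Discharge destination is already among the data reviewed for recovery under 3.3.2. The downside is a less favourable outcome for what is probably a handful of patients.
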